In all analyses, each patient will serve as their own control by comparing baseline measures with longitudinal results post-treatment. GDC-0449 may have little impact on inflammatory cell numbers in the peripheral blood or IHC specimens based on previous murine results [34]. Whether GDC-0449 will alter T cell cytokine profiles in circulation or in skin is unknown. Patients responding well to this SMO inhibitor may show reduced IL-17 and IFN γ in circulation as these cytokines have been associated with cutaneous manifestations of cGVHD [47]. These same studies showed Th2 cytokines (IL-4/13) were associated with aGVHD. If therapy fails to mediate clinical improvement, it may be due to an inability to inhibit these T cell responses. If GDC-0449 is effective, we anticipate reduced expression of GLI-1, GLI-2, PTCH-1 and PTCH-2 in skin. Because GLI-1 can activate IL-6 and IL-8 [63], these cytokines may be reduced in plasma post-GDC-0449 treatment and this may offer an assay to look for HH activity indirectly. Patients who do not respond may show no reductions in HH signaling (e.g. GLI-1) and this may indicate that drug levels were insufficient. It is also possible that patients may acquire SMO mutations that make them resistant to GDC-0449 [64, 65]. This could be determined by sequence analysis of SMO in those patients. We believe systemic markers of ECM synthesis, turnover and degradation will also be altered by GDC-0449 treatment in patients showing signs of clinical efficacy. We realize that these analyses are exploratory in nature given the relatively small sample size (n=12) for which CTEP agreed to provide study drug. However, these studies are highly significant as they are likely to identify relevant biomarkers that correlate with clinical efficacy or that may explain therapeutic futility. These will be critical insights into designing larger future trials.

14 ADVERSE EVENTS

14.1 Adverse Events / Serious Adverse Events

This study will utilize the CTCAE (NCI Common Terminology Criteria for Adverse Events) Version 4.0 for AE and SAE reporting. An electronic copy of the CTCAE Version 4.0 can be downloaded from: <http://safetyprofiler-ctep.nci.nih.gov/CTC/CTC.aspx>

14.1.1 Adverse Events (AE)

An adverse event is the appearance or worsening of any undesirable sign, symptom, or medical condition occurring after starting the study drug even if the event is not considered to be related to study drug. For the purposes of this study, the terms toxicity and adverse event are used interchangeably. Medical

conditions/diseases present before starting study drug are only considered adverse events if they worsen after starting study drug. Abnormal laboratory values or test results constitute adverse events only if they induce clinical signs or symptoms, are considered clinically significant, or require therapy.

The collection of adverse events will begin after the first dose of study treatment and end 30 days post the last dose of study treatment.

Information about all adverse events, whether volunteered by the subject, discovered by investigator questioning, or detected through physical examination, laboratory test or other means, will be collected and recorded and followed as appropriate.

The occurrence of adverse events should be sought by non-directive questioning of the patient at each visit or phone contact during the study. Adverse events also may be detected when they are volunteered by the patient during or between visits or through physical examination, laboratory test, or other assessments. As far as possible, each adverse event should be evaluated to determine:

1. the severity grade based on CTCAE v.4 (grade 1-5)
2. its relationship to the study drugs (definite, probable, possible, unlikely, not related)
3. its duration (start and end dates or if continuing at final exam)
4. action taken (no action taken; study drug dosage adjusted/temporarily interrupted; study drug permanently discontinued due to this adverse event; concomitant medication taken; non-drug therapy given; hospitalization/prolonged hospitalization)
5. whether it constitutes an SAE

All adverse events will be treated appropriately. Such treatment may include changes in study drug treatment as listed in the dose modification section of this protocol (see section 6 for guidance). Once an adverse event is detected, it should be followed until its resolution, or until the end of the follow-up period (6 months after removal from study treatment or until death, whichever occurs first) and assessment should be made at each visit (or more frequently, if necessary) of any changes in severity, the suspected relationship to the study drug, the interventions required to treat it, and the outcome.

Information about common side effects already known about the investigational drug is described in the Drug Information (section 3) and the most recent Investigator Brochure. This information will be included in the patient informed consent and will be discussed with the patient during the study as needed.

All adverse events will be immediately recorded in the patient research chart.

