6.1 Dose Modifications

In the case of any Grade 2 hematologic or non-hematologic toxicity attributable to the study drug, dose reductions can be performed to up to 3 different, consecutive levels as detailed below. All initial dose reductions will start at level -1, and proceed to the immediately lower level if the toxicity in question persists for at least 1 week. Dosing

schedules will be dependent on what day of the week the patient starts the dose reduction level; for example, patients on Dose Level -1 with a Monday start would dose on Wednesday, Friday, Sunday, and so on.

Dose reduction levels are:

- Level -1 (150 mg every other day)
 - Level -2 (150 mg every three days)
 - Level -3 (150 mg twice a week)
-
- GDC-0449 will be discontinued under the following circumstance:
 - Grade 3 or 4 non-hematologic or hematologic toxicity attributable to study treatment by Common Terminology Criteria for Adverse Events (CTCAE) version 4.

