9.2 Safety

Routine safety and tolerability will be evaluated from the results of reported signs and symptoms, scheduled physical examinations, vital sign measurements, and clinical laboratory test results. More frequent safety evaluations may be performed if clinically indicated or at the discretion of the investigator.

Physical Examination

Complete and symptom-directed physical examinations will be performed by a licensed physician (or physician's assistant or nurse practitioner).

Vital Signs

Vital signs (blood pressure, respiratory rate, pulse rate and temperature) will be obtained per the study calendar.

Safety Laboratory Determinations

Laboratory evaluations will be performed as noted on the study calendar.

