10.2 Sample Size/Accrual Rate/Other Statistical Considerations

Sample size: 12 patients. Accrual rate: 1-2 patients monthly.

This is a pilot study that will include 12 patients. FFS, the primary endpoint, will be evaluated using the Kaplan-Meier method. The impact of different covariates on FFS will be analyzed using descriptive statistics, t-test, and Fisher's exact test where applicable. Differences in NIH scores will be analyzed using Wilcoxon signed-rank test. Differences in biomarkers will be assessed using Wilcoxon rank-sum test.

Overall clinical response (PD, SD, PR, CR) according to NIH criteria will be tabulated and described based on organ response and overall response.

The proportion of subjects who experience adverse events and serious adverse events will be summarized descriptively; no inferential tests will be performed.

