15.3 Data and Safety Monitoring Plan

A Data and Safety Monitoring Committee (DSMC) is established at Huntsman Cancer Institute (HCI) and approved by the NCI to assure the well-being of patients enrolled on Investigator Initiated Trials that do not have an outside monitoring review. Roles and responsibilities of the DSMC are set forth in the NCI approved plan. The activities of this committee include a quarterly review of adverse events including SAEs, important medical events, significant revisions or amendments to the protocol, and approval of cohort/dose escalations. If the DSMC and/or the PI have concerns about unexpected safety issues, the study will be stopped and will not be resumed until the issues are resolved. The DSMC also reviews and approves audit reports generated by the Research Compliance Office.

This study will be reviewed by the full committee at each quarterly DSMC meeting. This includes a review of all serious adverse events (SAEs) occurring in patients treated at HCI or its affiliates as well as all grade 3 or greater toxicities for patients on treatment and within 30 days follow-up window (only if possibly, probably or definitely related).

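### Laboratory toxicity reaches the planned safety analysis only through an undefined judgement filter, and that filter does not fit the graded toxicity rules in Sections 6.1 and 15.3

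*Combined protocol and SAP*

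**What the plan says.** Five places in the combined protocol and SAP bear on this.

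- **Section 14.1.1** sets the vocabulary: "For the purposes of this study, the terms toxicity and adverse event are used interchangeably". It then limits which laboratory findings qualify: "Abnormal laboratory values or test results constitute adverse events only if they induce clinical signs or symptoms, are considered clinically significant, or require therapy". CTCAE severity is assigned to each adverse event, that is, to findings that have already qualified.
- **Section 6.1** has two dose rules, both worded in terms of toxicity. The first is permissive: "In the case of any Grade 2 hematologic or non-hematologic toxicity attributable to the study drug, dose reductions can be performed". The second makes discontinuation the consequence of "Grade 3 or 4 non-hematologic or hematologic toxicity attributable to study treatment by Common Terminology Criteria for Adverse Events (CTCAE) version 4".
- **Section 15.3** gives the full Data and Safety Monitoring Committee, each quarter, all serious adverse events and "all grade 3 or greater toxicities for patients on treatment and within 30 days follow-up window", restricted to those at least possibly related.
- **Section 9.2** says that routine safety is evaluated from several sources, among them "vital sign measurements, and clinical laboratory test results".
- **Section 10.2** contains the only safety analysis: "The proportion of subjects who experience adverse events and serious adverse events will be summarized descriptively". Section 10.4, on secondary endpoints, only refers back to 10.1.

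Safety is the first secondary endpoint listed in Section 10.1.2.

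**The concern.** Hematologic toxicity depends heavily on blood counts, and 6.1 names it. If the definition in 14.1.1 governs the word toxicity in 6.1 and 15.3, then a person's view of significance decides whether a graded count or liver enzyme value is seen by those rules at all. If it does not govern, the protocol has two meanings of one word. Either way, two staff members could handle the same value differently and both could cite the protocol.

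The analysis gap does not depend on which reading is right. Hematology and chemistry are drawn at every scheduled assessment visit, and 9.2 presents them as safety evidence, yet 10.2 has no table, listing or grade summary for them. What reaches the safety result is what someone chose to record as an event. The trial is open-label with a single arm, so that choice is made with knowledge of treatment and there is no comparator to show how selective it was.

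**Working it through.** The plan gives no figure to reproduce. The check is to follow one value through the text and then to show the scale.

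**Step 1: one value, two rules.** Take a Grade 3 neutrophil count that is attributed to the drug, causes no symptoms, is not treated, and is not called clinically significant by anyone.

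| Section | What it asks | Result for this value |
|---|---|---|
| 6.1, read alone | Attributed? CTCAE Grade 3 or 4? Hematologic or not? | A toxicity, and within the discontinuation rule |
| 14.1.1 | Symptoms or signs, or judged significant, or treated? | None is met, so not an adverse event |
| 14.1.1, terms | "the terms toxicity and adverse event are used interchangeably" | Not an adverse event, so not a toxicity |
| 15.3 | Related toxicity of Grade 3 or higher? | Depends on which meaning of toxicity applies |
| 10.2 | Adverse event or serious adverse event? | Not counted |

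The order also matters. Section 14.1.1 says that management of an adverse event may include dose changes under Section 6, so the event definition comes before the dose rules.

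**Step 2: route from laboratory data to the safety result.** Section 9.2 names laboratory results as a source. Section 10.2 analyses two quantities, the proportions with adverse events and with serious adverse events. No other analysis uses the laboratory values, so the only route is through 14.1.1.

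**Step 3: data already scheduled.** Section 7 and Section 8.2 place hematology and chemistry at months 1, 2, 3, 4 and 6 (5 sets), and at months 8, 10 and 12 for patients treated for a year (5 + 3 = 8 sets). If all 12 patients completed treatment this would be 12 × 5 = 60 to 12 × 8 = 96 sets. This counts blood draws, not abnormalities. Early withdrawal lowers it, and unscheduled visits raise it.

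**Step 4: scale at n = 12.** One patient is 1/12 = 8.3 percentage points. For a single laboratory toxicity, with exact two-sided 95% limits:

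- 0/12: upper limit = 1 − 0.025^(1/12) = 26.5%.
- 1/12: upper limit solves (1 − p)^12 + 12p(1 − p)^11 = 0.025, giving p = 38.5%.

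The plan itself calls for description only. The limits show how much one unrecorded patient weighs. They do not show that any patient will go unrecorded.

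**The case against.** The strongest case against is that the sections can be read together.

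- **The filter is an either/or test.** A value escapes only if it is silent *and* untreated *and* not judged significant. A drug-attributed Grade 3 or 4 value can readily be judged significant. This stands. A reader might infer that asymptomatic laboratory toxicity is excluded outright; the text supports only a discretionary filter.
- **Section 6.1 does not act on grade alone.** Both rules require attribution to study treatment, and the Grade 2 rule is permissive. Section 14.3.1 lists low neutrophils and platelets and raised ALT and AST among events with insufficient evidence of causation. This stands. A reader might infer that every Grade 3 value is a mandatory stop; without attribution it is not. The conflict is confined to attributed values.
- **Section 9.3 uses other terms.** Its safety reviews are triggered by a reaction, which 14.1.1 does not equate with adverse event, and its count from patient 05 onward is of discontinuations after Level -3. This stands. It cannot be said that 14.1.1 controls those reviews, only that reaction is undefined.
- **Laboratory results are in the safety evaluation through 9.2.** True, so it would be wrong to say that they bypass the safety endpoint. What is missing is a specified analysis. Case report forms and the cited reporting guidelines are not in the file, so it also cannot be said that grades go unrecorded.
- **The 0/12 contrast is artificial.** As an overall Grade 3 or higher rate it is. Section 2.5 reports that 57% of patients in the earlier basal-cell carcinoma trial had only Grade 1 or 2 events. If that rate applied here (an assumption, in a different population), the chance of no higher-grade patient in 12 would be 0.57^12, about 0.1%. The same section says that every patient there had at least one adverse effect, so the any-event proportion may not move at all. The contrast is meaningful only for a given laboratory toxicity. The any-event proportion, for the same reason, would say little about laboratory toxicity.

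None of this supplies the missing laboratory analysis or says which meaning of toxicity applies.

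**Conclusion.** The concern holds as an inconsistency between definitions and a gap in the analysis. Sections 14.1.1 and 6.1 can classify the same attributed Grade 3 or 4 laboratory value in opposite ways, with 15.3 depending on the same undefined point. Laboratory toxicity enters the planned safety summary only through a judgement for which neither a judge nor a grade criterion is stated.

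The conflict between definitions assumes that the synonym in 14.1.1 applies throughout the protocol, as its wording says. The analysis gap needs no such assumption.

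The number of patients affected cannot be estimated from the documents; each is 8.3 percentage points of any given rate. The direction is known: a filter that can only omit values can only lower reported laboratory toxicity. The definition of the primary endpoint, failure-free survival, does not use adverse events and is not in question. The point is worth acting on because the remedy uses blood tests already scheduled.

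**What to change.** 1. **Section 10.2.** Add a descriptive table, for each scheduled hematology and chemistry test, of baseline CTCAE grade against worst post-baseline CTCAE grade. Grade it from the values themselves, whether or not an adverse event was recorded. Baseline belongs in the table because Section 4.1.4 admits patients with platelets down to 50,000/mcL and AST or ALT up to 2.5 times the upper limit of normal.
2. **Sections 14.1.1, 6.1, 9.3 and 15.3.** Reconcile them by stating whether toxicity and reaction include CTCAE-graded laboratory values regardless of symptoms, and who judges clinical significance. Which values should change dosing is a clinical decision and is not proposed here.

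A simpler-looking remedy would be to record every worsened Grade 2 or higher value as an adverse event. Because toxicity and adverse event are synonyms in this protocol, that would also settle which attributed values trigger dose reduction or discontinuation, so it should not be adopted as a statistical fix.

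The cost is one table and a few sentences, with no extra blood draws. The downside is that reported laboratory toxicity may look slightly less favourable.

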14.1.2 Serious Adverse Event (SAE)

Information about all serious adverse events will be collected and recorded. Refer to section 14.3 for NCI serious adverse event guidelines.

14.2 Huntsman Cancer Institute SAE Reporting Requirements

SAEs must be reported to the DSMC, the FDA, the IRB, and the NCI, according to the requirements described below:

A CTEP-AERS form must be completed per NCI guidelines listed in section 14.3. At the completion of the online submission, the SAE report should be exported to a PDF and printed. The PI should sign and date the report which will then be submitted to [contact] as soon as possible, but no later than 10 days of first knowledge or notification of event (5 days for fatal or life threatening event).

DSMC Notifications:

- An HCI Research Compliance Officer (RCO) will process and submit the CTEP-AERS form to the proper DSMC member as necessary for each individual study.
- The RCO will summarize and present all reported SAEs according to the Data and Safety Monitoring Plan at the quarterly DSMC meeting.

IRB Notification:

- Events meeting the University of Utah IRB reporting requirements (<http://www.research.utah.edu/irb/>) will be submitted through the IRB's electronic reporting system within 10 working days.

14.3 CTEP Notification and Reporting Requirements

Adverse event (AE) monitoring and reporting is a routine part of every clinical trial. The following list of AEs and the characteristics of an observed AE will determine whether the event requires expedited reporting (via CTEP-AERS) **in addition** to routine reporting.

14.3.1 Comprehensive Adverse Events and Potential Risks List (CAEPR)

Comprehensive Adverse Events and Potential Risks list (CAEPR) for GDC-0449 (Vismodegib, NSC 747691)

The Comprehensive Adverse Events and Potential Risks list (CAEPR) provides a single list of reported and/or potential adverse events (AE) associated with an agent using a uniform presentation of events by body system. In addition to the comprehensive list, a subset, the Specific Protocol Exceptions to Expedited Reporting (SPEER), appears in a separate column and is identified with bold and italicized text. This subset of AEs (SPEER) is a list of events that are protocol specific exceptions to expedited reporting to NCI (except as noted below). Refer to the 'CTEP, NCI Guidelines: Adverse Event Reporting Requirements' http://ctep.cancer.gov/protocolDevelopment/electronic_applications/docs/aeguidelines.pdf for further clarification. *Frequency is provided based on 1893 patients.* Below is the CAEPR for GDC-0449 (Vismodegib).

NOTE: Report AEs on the SPEER **ONLY IF** they exceed the grade noted in parentheses next to the AE in the SPEER. If this CAEPR is part of a combination protocol using multiple investigational

agents and has an AE listed on different SPEERs, use the lower of the grades to determine if expedited reporting is required.

Version 2.5, December 22, 2016¹

Adverse Events with Possible Relationship to GDC-0449 (Vismodegib) (CTCAE 4.0 Term) [n= 1893]			Specific Protocol Exceptions to Expedited Reporting (SPEER)
Likely (>20%)	Less Likely (<=20%)	Rare but Serious (<3%)	
GASTROINTESTINAL DISORDERS			
	Abdominal pain		
	Constipation		
	Diarrhea		Diarrhea (Gr 2)
	Dyspepsia		
	Nausea		Nausea (Gr 3)
	Vomiting		
GENERAL DISORDERS AND ADMINISTRATION SITE CONDITIONS			
Fatigue			Fatigue (Gr 3)
INVESTIGATIONS			
	CPK increased		
Weight loss			Weight loss (Gr 2)
METABOLISM AND NUTRITION DISORDERS			
Anorexia	Dehydration		Anorexia (Gr 3)
MUSCULOSKELETAL AND CONNECTIVE TISSUE DISORDERS			
	Arthralgia		
Musculoskeletal and connective tissue disorder - Other (muscle spasms/twitching)			Musculoskeletal and connective tissue disorder - Other (muscle spasms/twitching) (Gr 2)
		Musculoskeletal and connective tissue disorder - Other (premature epiphyseal closure)	
NERVOUS SYSTEM DISORDERS			
Dysgeusia			Dysgeusia (Gr 2)
REPRODUCTIVE SYSTEM AND BREAST DISORDERS			
Irregular menstruation ²			Irregular menstruation² (Gr 2)
SKIN AND SUBCUTANEOUS TISSUE DISORDERS			
Alopecia			Alopecia (Gr 2)

¹This table will be updated as the toxicity profile of the agent is revised. Updates will be distributed to all Principal Investigators at the time of revision. The current version can be obtained by contacting [contact]. Your name, the name of the investigator, the protocol and the agent should be included in the e-mail.

²Irregular menstruation was observed in 30% (3 of 10) women of child bearing age and/or in 28% (18 of 64) women who had menses at baseline who were enrolled in studies of advanced BCC.

³Gastrointestinal hemorrhage includes Anal hemorrhage, Cecal hemorrhage, Colonic hemorrhage, Duodenal hemorrhage, Esophageal hemorrhage, Esophageal varices hemorrhage, Gastric hemorrhage, Hemorrhoidal hemorrhage, Ileal hemorrhage, Intra-abdominal hemorrhage, Jejunal hemorrhage, Lower gastrointestinal hemorrhage, Oral hemorrhage, Pancreatic hemorrhage, Rectal hemorrhage, Retroperitoneal hemorrhage, and Upper gastrointestinal hemorrhage under the GASTROINTESTINAL DISORDERS SOC.

⁴Infection includes all 75 sites of infection under the INFECTIONS AND INFESTATIONS SOC.

Adverse events reported on GDC-0449 (Vismodegib) trials, but for which there is insufficient evidence to suggest that there was a reasonable possibility that GDC-0449 (Vismodegib) caused the adverse event:

BLOOD AND LYMPHATIC SYSTEM DISORDERS - Anemia; Febrile neutropenia; Thrombotic thrombocytopenic purpura

CARDIAC DISORDERS - Atrial fibrillation; Atrial flutter; Cardiac arrest; Heart failure; Myocardial infarction; Pericardial tamponade; Sinus bradycardia

EYE DISORDERS - Keratitis; Retinal vascular disorder

GASTROINTESTINAL DISORDERS - Abdominal distension; Ascites; Dry mouth; Dysphagia; Esophageal pain; Esophagitis; Flatulence; Gastritis; Gastroesophageal reflux disease; Gastrointestinal disorders - Other (thrush); Gastrointestinal hemorrhage³; Gastrointestinal pain; Ileus; Mucositis oral; Pancreatitis; Stomach pain

GENERAL DISORDERS AND ADMINISTRATION SITE CONDITIONS - Edema limbs; Facial pain; Fever; Injection site reaction; Non-cardiac chest pain; Pain

HEPATOBIILIARY DISORDERS - Cholecystitis; Hepatic failure; Portal hypertension

INFECTIONS AND INFESTATIONS - Infection⁴

INJURY, POISONING AND PROCEDURAL COMPLICATIONS - Bruising; Hip fracture

INVESTIGATIONS - Alanine aminotransferase increased; Alkaline phosphatase increased; Aspartate aminotransferase increased; Blood bilirubin increased; Cholesterol high; Creatinine increased; GGT increased; INR increased; Investigations - Other (brain natriuretic peptide increased); Investigations - Other (elevated LDH); Lipase increased; Lymphocyte count decreased; Neutrophil count decreased; Platelet count decreased; White blood cell decreased

METABOLISM AND NUTRITION DISORDERS - Hypercalcemia; Hyperglycemia; Hyperkalemia; Hypermagnesemia; Hyponatremia; Hypoalbuminemia; Hypocalcemia; Hypoglycemia; Hypokalemia; Hypomagnesemia; Hyponatremia; Hypophosphatemia

MUSCULOSKELETAL AND CONNECTIVE TISSUE DISORDERS - Arthritis; Back pain; Flank pain; Generalized muscle weakness; Muscle weakness lower limb; Musculoskeletal and connective tissue disorder - Other (muscle tightness/stiffness); Myalgia; Neck pain; Pain in extremity; Trismus

NEOPLASMS BENIGN, MALIGNANT AND UNSPECIFIED (INCL CYSTS AND POLYPS) - Leukemia secondary to oncology chemotherapy; Treatment related secondary malignancy

NERVOUS SYSTEM DISORDERS - Ataxia; Cognitive disturbance; Dizziness; Dysesthesia; Headache; Intracranial hemorrhage; Movements involuntary; Nervous system disorders - Other (amimia); Olfactory nerve disorder; Paresthesia; Peripheral motor neuropathy; Peripheral sensory neuropathy; Seizure; Stroke; Syncope; Tremor

PSYCHIATRIC DISORDERS - Agitation; Anxiety; Confusion; Depression; Hallucinations; Insomnia; Psychosis

RENAL AND URINARY DISORDERS - Acute kidney injury; Renal hemorrhage

REPRODUCTIVE SYSTEM AND BREAST DISORDERS - Erectile dysfunction

RESPIRATORY, THORACIC AND MEDIASTINAL DISORDERS - Aspiration; Cough; Dyspnea; Epistaxis; Hiccups; Hypoxia; Pleural effusion; Pneumonitis; Postnasal drip; Pulmonary edema; Respiratory, thoracic and mediastinal disorders - Other (COPD); Respiratory, thoracic and mediastinal disorders - Other (oropharyngeal pain); Sneezing; Sore throat

SKIN AND SUBCUTANEOUS TISSUE DISORDERS - Hyperhidrosis; Nail ridging; Pruritus; Rash acneiform; Rash maculo-papular; Skin and subcutaneous tissue disorders - Other (hair color changes); Skin and subcutaneous tissue disorders - Other (psoriasis); Skin and subcutaneous tissue disorders - Other (skin exfoliation); Skin ulceration; Stevens-Johnson syndrome

VASCULAR DISORDERS - Hypertension; Hypotension; Thromboembolic event; Vasculitis

Note: GDC-0449 (Vismodegib) in combination with other agents could cause an exacerbation of any adverse event currently known to be caused by the other agent, or the combination may result in events never previously associated with either agent.

Additional Adverse Events

Serious or Life-threatening Birth Defect Effects of GDC-0449

Studies have demonstrated that inhibition of the Hh pathway in embryos results in brain, facial, and other midline defects, including holoprosencephaly or microencephaly, cyclopia, absent nose, cleft palate, tooth abnormalities, and bone development abnormalities (Bale, 2002). While the effects of GDC-0449 on the developing human fetus at the recommended therapeutic dose are unknown, women of childbearing potential and men must agree to use two methods of contraception (i.e., barrier contraception and another method of contraception) prior to study entry, for the duration of study participation, and for 24 months following treatment.

Women of childbearing potential are defined as follows:

- Patients with regular menses

- Patients with amenorrhea, irregular cycles, or using a contraceptive method that precludes withdrawal bleeding
- Women who have had a tubal ligation

Women are considered not to be of childbearing potential for the following reasons:

- The patient has undergone hysterectomy and/or bilateral oophorectomy.
- The patient is post-menopausal defined by amenorrhea for at least 12 months in a woman > 45 years old.

Women of childbearing potential are required to use two forms of acceptable contraception (refer to [Appendix B](#)), including one barrier method during participation in the study and for the 24 months following the last dose. All patients should receive contraceptive counseling either by the investigator or by an OB/gynecologist or other physician who is qualified in this area of expertise. If a woman of childbearing potential believes that her contraceptive method has failed, emergency contraception should be considered.

If a patient is suspected to be pregnant, GDC-0449 should be IMMEDIATELY discontinued and the study physician contacted. A positive urine test must be confirmed by a serum pregnancy test. If it is confirmed that the patient is not pregnant, the patient may resume dosing with GDC-0449.

If a female patient becomes pregnant during therapy or within 24 months after the last dose of GDC-0449, or if the female partner of a male patient exposed to the drug becomes pregnant while the male patient is receiving GDC-0449 or within 3 months after the last dose of GDC-0449, the investigator must be notified in order to facilitate outcome follow-up.

Abortion, whether accidental, therapeutic, or spontaneous, should always be classified as serious. Any congenital anomaly/birth defect in a child conceived during the study or within 24 months after the last dose of GDC-0449 to a female patient or to a female partner of a male patient exposed to the agent during treatment or within 3 months after the last dose of GDC-0449 should be recorded and reported as an SAE.

In addition, it is not known whether GDC-0449 that may be present in seminal fluid would cause serious or life-threatening birth defects in a fetus born to the female partner of a male subject. Sexually active male subjects should utilize a barrier form of contraception, even those who have had a vasectomy, during study treatment and for 3 months after the last dose. Male patients should advise their partners to use an additional method of contraception during the study and for at least 3 months after discontinuation of GDC-0449. Male subjects should also not donate sperm during treatment or up to 12 months after the last dose.

Risk of Male Germ Cell Degeneration

[REDACTED]

